5.4.1. Independent Data Monitoring Committee

An IDMC will monitor the safety aspects of *Boostrix* in the clinical study. An IDMC including an obstetrician, paediatrician, statistician and a neonatologist will be in charge of monitoring the safety aspects of the study and the committee will meet at regular intervals to review data on other adverse pregnancy outcomes. The frequency of the meeting will be decided in consultation with the chairman of the committee.

To facilitate the review, the IDMC will be provided with all relevant safety data including data on congenital anomaly/foetal malformation/ incidence of grade 3 local and general solicited adverse events, withdrawals due to adverse experiences and SAE data at specified times and access to data on request by an unblinded statistician. The GSK staff and other study staff will be blinded during this study.

The IDMC will have access to the individual codes and may at its discretion, decode the cases to identify the product administered to any subject and evaluate whether enrolment in the study should be halted or if any additional safety follow-ups are required for subject safety.

The operating rules of the IDMC will be established by GSK and will be documented by a charter.

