10.3. Determination of sample size

It is proposed to conduct the study with a sample size of 680 subjects. Assuming a drop-out rate of approximately 20%, to compensate for subject attrition due to early withdrawal, a total of 680 subjects (340 in each group) will be randomised in a 1:1 ratio in order to obtain the desired number of 272 evaluable subjects in each group for immunogenicity analysis. Availability of 272 evaluable subjects per group (for a total of 680 subjects) will provide above 96% overall power to reach the primary endpoint for the primary maternal phase using Bonferroni adjustment on type II error. This sample size is justified by the expected difficulty to enrol pregnant women in the study and on the minimum requirement of safety data in pregnant women, as determined by EU guidelines [EMA, 2008].

Table 16 presents the Power to rule out the null hypothesis (H_0 : group GMC ratio < 1.5) that dTpa Group is not superior to the Control Group.

Table 16 Power to rule out the null hypothesis (H_0 : group GMC ratio < 1.5) that dTpa Group is not superior to the Control Group (N= 272 evaluable subjects per group)

Endpoint	Standard deviation* [Log ₁₀ (titre)]	True group ratio*	Power**
Anti-PT	0.577	2.3	96%
Anti-FHA	0.564	5	>99%
Anti-PRN	0.564	5	>99%

*anticipated conservative value (References: [Leuridan, 2011; Munoz, 2014])

** PASS2005, one sided test for difference between 2 independent groups, H_A : group difference=log10 (true group ratio), one-side alpha = 0.025, Assuming common variance between the groups Using Bonferroni adjustment on type II error (overall beta=sum of type II error of each endpoint)

Table 17 presents the precision achieved with a sample of 300 subjects in each group for the various possible expected adverse pregnancy outcomes and listed pregnancy-related adverse events of interest/neonate-related events of interest in terms of exact 95% CIs.

Table 17 Precision achieved with a sample of 300 subjects in each group for the various possible expected pregnancy outcomes and listed pregnancy-related adverse events of interest/ neonate-related events of interest in terms of exact 95 percent CI

No. of subjects expected (N)	Pregnancy outcome and listed pregnancy-related adverse events of interest/neonate-related events of interest	Subjects with outcome			
		n	%	Exact 95%CI	
				LL	UL
300	Stillbirth	1	0.3	0.0	1.8
	Stillbirth [^]	0	0.0	0.0	1.2
	Placental Abruption	3	1.0	0.2	2.9
	Placenta previa	1	0.3	0.0	1.8

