Handling of missing data: For a given subject and a given immunogenicity measurement, missing or non-evaluable measurements will not be replaced.

Safety/ Reactogenicity

- For the analysis of solicited symptoms, missing or non-evaluable measurements will not be replaced. Therefore the analysis of the solicited symptoms based on the TVC will include only subjects with documented safety data (i.e. symptom screen completed).
- For the analysis of unsolicited symptoms, SAEs and analyses that combine solicited and unsolicited symptoms, subjects with no report of the event will be considered to have not had the event. Subjects who do not report being administered concomitant medications and vaccinations will be considered to have not received any medications and vaccinations.

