## 6.4. Analysis of safety

### 6.4.1. Analysis of safety planned in the protocol

The primary analysis will be performed on the TVC. If in any vaccine group, 5% or more of the vaccinated subjects are eliminated from the TVC, a second analysis will be performed on the ATP cohort for analysis of safety. Analysis of safety in household contacts will be performed on the Total cohort for household contacts in Spain.

- The percentage of subjects with each specific pregnancy outcomes and listed pregnancy-related adverse events of interest/neonate-related events of interest will be tabulated with its exact 95% CI.
- The percentage of subjects with at least one local AE (solicited and unsolicited), with at least one general AE (solicited and unsolicited) and with any AE during the 8-day (Day 0–Day 7) follow-up period after the vaccination will be tabulated after each dose with exact 95% CI. The same calculations will be performed for any Grade 3 (solicited or unsolicited) symptoms, any causal relationship to vaccination and for any symptoms requiring medical attention.
- The percentage of subjects reporting each individual solicited local and general AE during the 8-day (Day 0–Day 7) follow-up period after booster vaccination will be tabulated with its exact 95% CI for each group.
- All computations mentioned above will be done for Grade  $\geq 2$  (solicited symptoms only) and Grade 3 symptoms, for symptoms considered related to vaccination (general symptoms only), for Grade 3 symptoms considered related to vaccination (general symptoms only) and for symptoms that resulted in a medically-attended visit.
- Occurrence of fever and related fever will be reported per 0.5°C cumulative temperature increments as well as the occurrence of Grade 3 fever ( $> 39.0^{\circ}\text{C}$  axillary temperature) with causal relationship to vaccination.
- Any large injection site reaction (defined as any local swelling with diameter  $> 100$  mm and/or any noticeable diffuse injection site swelling (diameter not measurable) and/or any noticeable increased circumference of the injected limb) onset within 8 days (Day 0–Day 7) after each vaccination will be described in detail.

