## 11.2.5. Safety analysis

### 11.2.5.1. Solicited Adverse Events

For analysis of solicited, unsolicited adverse events (such as serious adverse events or adverse events by primary MedDRA term) and for the analysis of concomitant medications, all vaccinated subjects will be considered. Subjects who did not report the event or the concomitant medication will be considered as subjects without the event or the concomitant medication respectively.

The following rules will be used for the analysis of solicited symptoms:

- Subject who didn't document the presence or absence of a solicited symptom after one dose will be considered not having that symptom after that dose in the analysis done on "administered dose"
- Subjects who documented the absence of a solicited symptom after one dose will be considered not having that symptom after that dose.
- Subjects who documented the presence of a solicited symptom and fully or partially recorded daily measurement over the solicited period will be included in the summaries at that dose and classified according to their maximum observed daily recording over the solicited period.
- Subjects who documented the presence of a solicited symptom after one dose without having recorded any daily measurement will be considered as having that symptom after that dose (at the lowest intensity).
- Intensity of the following solicited AEs will be assessed as described below.

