**Table 5 Intensity scales for solicited symptoms in adults**

Adverse Event	Intensity grade	Parameter
Pain at injection site	0	None
	1	Mild: Any pain neither interfering with nor preventing normal every day activities.
	2	Moderate: Painful when limb is moved and interferes with every day activities.
	3	Severe: Significant pain at rest. Prevents normal every day activities.
Redness at injection site		Record greatest surface diameter in mm
Swelling at injection site		Record greatest surface diameter in mm
Fever*		Record temperature in °C/°F
Headache	0	Normal
	1	Mild: Headache that is easily tolerated
	2	Moderate: Headache that interferes with normal activity
	3	Severe: Headache that prevents normal activity
Fatigue	0	Normal
	1	Mild: Fatigue that is easily tolerated
	2	Moderate: Fatigue that interferes with normal activity
	3	Severe: Fatigue that prevents normal activity
Gastrointestinal symptoms (nausea, vomiting, diarrhoea and/or abdominal pain)	0	Normal
	1	Mild: Gastrointestinal symptoms that are easily tolerated
	2	Moderate: Gastrointestinal symptoms that interfere with normal activity
	3	Severe: Gastrointestinal symptoms that prevent normal activity

\*Fever is defined as temperature  $\geq 37.5^{\circ}\text{C}$  /  $99.5^{\circ}\text{F}$  for oral, axillary or tympanic route, or  $\geq 38.0^{\circ}\text{C}$  /  $100.4^{\circ}\text{F}$  for rectal route. The preferred route for recording temperature in this study will be oral/axillary.

The maximum intensity of local injection site redness/swelling/fever will be scored at GSK Biologicals as follows:

- 0 : Absent  
 1 :  $\leq 20$  mm  
 2 :  $> 20$  mm and  $\leq 50$  mm  
 3 :  $> 50$  mm

Event	N used for deriving % per subject for Vaccination phase	N used for deriving % per dose for Vaccination phase
Concomitant vaccination	All subjects with study vaccine administered	All study visits with study vaccine administered
Solicited general symptom	Primary analysis: all subjects with study vaccine administered Sensitivity analysis: all subjects with at least one solicited general symptom documented as either present or absent (i.e., symptom screen completed)	Primary analysis: all study visits with study vaccine administered Sensitivity analysis: all study visits with study vaccine administered and with at least one solicited general symptom documented as either present or absent (i.e., symptom screen completed)

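### A solicited symptom reported with no daily value is scored at the lowest intensity, so the planned Grade ≥2 and Grade 3 percentages are lower bounds and should be shown as such

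*SAP*

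**What the plan says.** SAP 11.2.5.1 treats a symptom documented as present in two ways. If any daily values exist, even a partial set, the woman is "classified according to their maximum observed daily recording over the solicited period". If none exist, a woman who reported the symptom "without having recorded any daily measurement will be considered as having that symptom after that dose (at the lowest intensity".

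SAP 6.4.1 turns these classifications into severity tables: "All computations mentioned above will be done for Grade" ≥2 (solicited symptoms only) and for Grade 3. The percentages carry exact 95% confidence intervals and are given for each dose.

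The denominators are in the table that follows the intensity scales (SAP Table 5). For solicited general symptoms the rule is "Primary analysis: all subjects with study vaccine administered". One sensitivity analysis is planned, on "all subjects with at least one solicited general symptom documented as either present or absent (i.e., symptom screen completed". That table has no row for local symptoms, but the opening of 11.2.5.1 takes all vaccinated subjects for solicited events generally.

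Protocol 10.5 states: "For the analysis of solicited symptoms, missing or non-evaluable measurements will not be replaced". It then draws the consequence that the solicited-symptom analysis covers only women with a completed symptom screen. SAP Section 9 describes the assay change and refers to 6.1.2, 6.3.2 and 6.4.2 for the rest. None of these mentions the intensity rule.

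**The concern.** Here the symptom is known to have occurred and only its severity is missing. Giving it the mildest grade is a best-case imputation, and the tables as planned would not show how many grades were observed and how many were assigned.

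Missing need not mean mild. Swelling is graded only by diameter in millimetres. Yet Protocol 8.1.3.1 and SAP 6.4.1 recognise, as a form of large injection site reaction, diffuse swelling whose diameter cannot be measured. If no diameter is recorded on any day for that reason, the rule scores the swelling as Grade 1 (≤20 mm). The reaction would still be described separately, but the Grade ≥2 and Grade 3 swelling rows would miss it.

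Reactogenicity is a stated secondary objective. Where severe symptoms are rare, a few records can change a printed percentage and its upper limit noticeably.

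**Working it through.** **Inputs**
- N = 340 per group. Protocol 10.3: "a total of 680 subjects (340 in each group) will be randomised in a 1:1 ratio". This agrees with 272 evaluable women after 20% attrition: 272/(1 − 0.20) = 340.
- Intervals: Clopper-Pearson, two-sided 95% (SAP 11.1).
- g = women with an observed value at the grade. Not in the documents; illustrated with 0, 3 and 17.
- m = women with the symptom present and no daily value. Not in the documents; assumed 1 to 7.

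The plan states no figure that depends on this rule, so there is none to reproduce.

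**Bounds.** The planned rate is g/N. If all m were truly below the grade, the full-data rate is also g/N. If all m were at the grade, it is (g+m)/N. The error is therefore downward or zero, and at most m/N:
- m = 1: 1/340 = 0.3 points
- m = 3: 3/340 = 0.9 points
- m = 7: 7/340 = 2.1 points

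| g | m | Planned rate (95% CI) | All unknowns at the grade (95% CI) |
|---|---|---|---|
| 0 | 3 | 0.0% (0.0–1.1) | 0.9% (0.2–2.6) |
| 3 | 3 | 0.9% (0.2–2.6) | 1.8% (0.7–3.8) |
| 3 | 7 | 0.9% (0.2–2.6) | 2.9% (1.4–5.3) |
| 17 | 7 | 5.0% (2.9–7.9) | 7.1% (4.6–10.3) |

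**A milder assumption.** If only a share s of the unknowns were truly Grade 3, the expected loss is m·s/N. With s = 10% (assumed), it is 3 × 0.10/340 = 0.09 points for m = 3 and 7 × 0.10/340 = 0.2 points for m = 7.

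**Does the sensitivity analysis help?** No. It restricts the denominator to women with at least one general symptom documented as present or absent. A woman who marked a general symptom as present satisfies that, so she stays in, still at the lowest intensity.

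**Does non-replacement under Protocol 10.5 give a different answer?** Take g = 3, m = 3:
- SAP rule: 3/340 = 0.88%.
- Intensity left missing, woman kept in the denominator: 3/340 = 0.88%.
- Intensity left missing, woman dropped from the graded rows: 3/337 = 0.89%.

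The Grade 3 numerator is the same in all three. Only explicit reporting of the unknowns shows the range.

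**The case against.** The best defence is that the rule is pre-specified openly in the annex of standard derivations, is narrow, and probably affects few women. It applies only when no day at all is recorded, because partial records use the observed maximum. Protocol 5.6.1.3.9 has diary cards collected and verified in discussion with the woman at Visits 2, 3 and 4. Large injection site reactions are evaluated by the investigator and described in detail, and medically attended symptoms are tabulated separately. All of this stands and limits the likely size. It does not make the graded percentages anything other than a lower bound.

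A reader might infer that the SAP contradicts Protocol 10.5 and that the protocol rule would give higher Grade 3 rates. The second part fails, because non-replacement leaves the numerator unchanged. The first part is arguable: the protocol sentence can be read as governing who is included, and the protocol has no explicit rule for presence without intensity. Still, assigning a grade does replace a missing measurement, and Section 9 does not mention it, so listing the rule there is reasonable.

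A reader might also infer that safety monitoring during the trial was affected, since Protocol 5.4.1 lists "incidence of grade 3 local and general solicited adverse events" among the data for the monitoring committee. The documents do not show this. In-study review runs under a separate charter, and the SAP, dated 20 February 2018, schedules only a final analysis. The one documented link is that the committee reviews that final analysis (Protocol 5.4.2).

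**Conclusion.** The point holds as a minor one. The planned Grade ≥2 and Grade 3 percentages for solicited symptoms equal the minimum of the range g/N to (g+m)/N, so they are understated or, at best, correct. The understatement cannot exceed m/340 per group: 0.3, 0.9 or 2.1 points for an assumed m of 1, 3 or 7. Those maxima require every unknown to be at the grade. If m is zero, nothing changes.

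It is tempting to add that the loss must be larger after Boostrix, because more symptoms give more opportunity for downgrading, and that the severity contrast with placebo is therefore shrunk. That needs assumptions about the missing share and true severity in each group, and the documents supply neither. The rule applies to both groups, the safety objectives are descriptive (SAP Section 7), and no between-group severity test is planned.

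The any-intensity percentages, the primary cord-blood comparison, its type I error and its power do not depend on this rule.

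**What to change.** - In SAP 11.2.5.1, remove the assignment to the lowest intensity and state that such a symptom is counted in the any-intensity row with intensity unknown.
- Report the number with unknown intensity by symptom, dose and group. A footnote is enough where it is zero.
- Keep the planned Grade ≥2 and Grade 3 percentages, labelled as lower bounds. Where the number is above zero, add one sensitivity row counting the unknowns at the grade, as the upper bound.
- List the rule in SAP Section 9, with a line on how it relates to Protocol 10.5.

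Cost: SAP wording and a footnote or one extra row in the solicited-symptom tables. No new data are needed. Where unknowns exist, the Grade 3 upper bound will look slightly less favourable.

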**Table 5 Intensity scales for solicited symptoms in adults**

Adverse Event	Intensity grade	Parameter
Pain at injection site	0	None
	1	Mild: Any pain neither interfering with nor preventing normal every day activities.
	2	Moderate: Painful when limb is moved and interferes with every day activities.
	3	Severe: Significant pain at rest. Prevents normal every day activities.
Redness at injection site		Record greatest surface diameter in mm
Swelling at injection site		Record greatest surface diameter in mm
Fever*		Record temperature in °C/°F
Headache	0	Normal
	1	Mild: Headache that is easily tolerated
	2	Moderate: Headache that interferes with normal activity
	3	Severe: Headache that prevents normal activity
Fatigue	0	Normal
	1	Mild: Fatigue that is easily tolerated
	2	Moderate: Fatigue that interferes with normal activity
	3	Severe: Fatigue that prevents normal activity
Gastrointestinal symptoms (nausea, vomiting, diarrhoea and/or abdominal pain)	0	Normal
	1	Mild: Gastrointestinal symptoms that are easily tolerated
	2	Moderate: Gastrointestinal symptoms that interfere with normal activity
	3	Severe: Gastrointestinal symptoms that prevent normal activity

\*Fever is defined as temperature  $\geq 37.5^{\circ}\text{C}$  /  $99.5^{\circ}\text{F}$  for oral, axillary or tympanic route, or  $\geq 38.0^{\circ}\text{C}$  /  $100.4^{\circ}\text{F}$  for rectal route. The preferred route for recording temperature in this study will be oral/axillary.

The maximum intensity of local injection site redness/swelling/fever will be scored at GSK Biologicals as follows:

- 0 : Absent  
 1 :  $\leq 20$  mm  
 2 :  $> 20$  mm and  $\leq 50$  mm  
 3 :  $> 50$  mm

Event	N used for deriving % per subject for Vaccination phase	N used for deriving % per dose for Vaccination phase
Concomitant vaccination	All subjects with study vaccine administered	All study visits with study vaccine administered
Solicited general symptom	Primary analysis: all subjects with study vaccine administered Sensitivity analysis: all subjects with at least one solicited general symptom documented as either present or absent (i.e., symptom screen completed)	Primary analysis: all study visits with study vaccine administered Sensitivity analysis: all study visits with study vaccine administered and with at least one solicited general symptom documented as either present or absent (i.e., symptom screen completed)
Unsolicited symptom	All subjects with study vaccine administered	All study visits with study vaccine administered
Concomitant medication	All subjects with study vaccine administered	All study visits with study vaccine administered

Body temperature will be broken down by route of measurement according to the recommendations of the Brighton collaboration and will be summarized according to the 2 schemes described below:

- by 0.5 °C increments:
  - $\geq 37.5$
  - $\geq 38.0$
  - $> 38.5$
  - $> 39.0$
  - $> 39.5$
  - $> 40.0$

Fever, defined as a body temperature of  $\geq 37.5^{\circ}\text{C}$  irrespective of route of measurement, will be integrated to the summaries as a systemic adverse event.

#### 11.2.5.2. Combined Solicited and Unsolicited Adverse Events

A summary of subjects with all combined solicited (regardless of their duration) and unsolicited adverse events will be provided. Solicited adverse events will be coded by MedDRA as per the following codes.

Solicited symptom	Lower level term code	Corresponding Lower level term decode
Fever	10016558	Fever
Headache	10019211	Headache
Fatigue	10016256	Fatigue
Gastrointestinal symptoms (nausea, vomiting, diarrhoea and/or abdominal pain)	10017944	Gastrointestinal disorder
Pain at injection site	10022086	Injection site pain
Redness at injection site	10022098	Redness at injection site
Swelling at injection site	10053425	Swelling at injection site

For clintrial.gov and EudraCT posting purposes, a summary of combined solicited and unsolicited non-serious adverse events will be produced by System Organ Class and preferred terms and according to occurrence of each event.

**11.2.6. Management of missing data****Demography:**

- For a given subject and a given demographic variable, missing measurements will not be replaced.

**Immunogenicity:**

- For a given subject and a given immunogenicity measurement time point, missing or non-evaluable measurements will not be replaced.

**Reactogenicity and safety:**

- Subjects who missed reporting symptoms (solicited/unsolicited or concomitant medications) will be treated as subjects without symptoms (solicited/unsolicited or concomitant medications, respectively).

**11.2.7. Number of decimals displayed**

The following decimal description from the decision rules will be used for the demography, immunogenicity and safety/reactogenicity.

Display Table	Parameters	Number of decimal digits
All summaries	% of count, including LL & UL of CI	1
All summaries	% of difference, including LL & UL of CI	2
Demographic characteristics	Mean, median age, SD (age)	1
Reactogenicity	Mean, Min, Q1, Median, Q3, Max for duration	1
Immunogenicity	Ratio of GMT/GMC	2
Immunogenicity	GMC	2 ( D and T) 1 (PT, FHA and PRN)

## **12. ANNEX 3: STUDY SPECIFIC MOCK TFL**

The following draft study specific mock TFLs will be used.

The data display, title and footnote are for illustration purpose and will be adapted to the study specificity such as one group and one dose for the study.

These templates were copied from recent studies. Note that there may be few changes between the study specific SAP mock TFL and the final TFLs. These editorial/minor changes will not lead to a SAP amendment.

